There is no data available at the institution to support the sample size justification based on efficacy of this treatment combination. **In the published literature, the objective response rate to Dabrafenib and Trametinib using RECIST 1.1 Criteria is 76% (N=54, 95% CI, 65% to 87%)¹ (Flaherty et al, NEJM, 367:1694, 2012).** We expect that the overall response rate should be between 60-80%. Therefore an objective response rate less than 64% should indicate the treatment is not sufficiently promising ($P_0 = 0.64$); this is a bit lower than the lower limit of the 95% CI. We expect the therapy to increase the overall response rate at 80% ($P_1 = 0.80$). Using Simon's two stage minimax design for phase II trials we plan to enroll a maximum of 53 patients. In first stage, 20 patients will be enrolled. Table S1 gives the details of the justification of this sample size. Note that if the treatment is not altered in Phase I, patients enrolled on Phase I will be included in Phase II in the efficacy estimation.

Table S1. Sample size justification $P_0 = 0.64$, $P_1 = 0.80$, $\alpha = 0.05$ and power = 80%

MiniMax Two Stage Design	MiniMax Design
First Stage Sample Size (n1)	20
Upper Limit For 1 st Stage Rejection of Drug (# of OR)	13
Maximum Sample Size (n)	53
Upper Limit for 2 nd Stage Rejection of Drug (# of OR)	39
Expected Sample Size If Response Probability = 0.64	33
Probability of Early Termination at If RP=0.64	0.62

6.4 Accrual Rate:

Based on our experience we plan to enroll 30 patients per year. It will take approximately 2.0 years to complete the enrollment of 53 patients. Depending on the treatment's performance we may not need to enroll all 53 participants. Given the relatively short overall survival times, all patients will be followed for up to 3 years once enrolled and after the end of treatment with Dabrafenib/Trametinib/Metformin.

6.5 Statistical Analysis:

General Approach:

Patients receiving treatment will be presented. Patients receiving treatment who are found not to have fully met the eligibility criteria will be presented. On-study protocol violations will also be presented. Patients who do not complete the required observations will be listed and evaluated separately as necessary. Reasons for study discontinuation and date of withdrawal from study will be presented.

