We will estimate the overall survival (OS) rates using the method of Kaplan-Meier. To compare the results with historical controls (results published in NEJM, 2011 and others), we need to estimate fixed term (such as 1-year, 2-year) OS rate along with 95% confidence interval precisely, that we plan to do using the method of Yuan and Rai (2011)³¹

- *To describe the toxicities.*

We will produce frequency and percentages of different CTCAE.

- *To explore the effect of other covariates (demographic, disease and treatment related) on objective response rate and toxicity and overall survival.*

We will identify the covariates and define specific groups, using some cut-offs, that are meaningful in a regression analysis. The effect of the covariates on a dichotomous outcome (OR or Toxicity) and time-to-event (OS) will be explored using a logistic regression and Cox proportional Hazards model, respectively.

6.6 Monitoring Rule for Phase II:

Safety monitoring of the accumulated outcomes data is designed to ensure the continuing safety of the currently enrolled participants and participants not yet enrolled. This is achieved by stopping the trial early to reduce the number of participants exposed to a harmful or ineffective treatment.

6.7 Non-efficacious Treatment (Futility):

In the combined regimen Dabrafenib/Trametinib/Metformin: in the first stage we will enroll 28 participants and if we observe at most 12 objective responses we will not enroll any new participants. If we observe 13 or more objective responses in the first stage, then we plan to enroll an additional 25 patients. In order for the treatment to be declared effective there has to be objective responses in at least 29 patients. If the objective response rate is only 41%, we will have 66% chance of stopping the study early and, at most, 37 patients will be treated on the potentially ineffective therapy.

6.8 Toxic Treatment (Safety) for Combined Phase I/II Trial:

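### Section 6.7 states the expected sample size of its futility rule (37 at a 41% response rate) as a maximum; the rule's own maximum is 53

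*Combined protocol and SAP*

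**What the plan says.** Section 6.7 sets out a two-stage futility rule. Its first step is "in the first stage we will enroll 28 participants", and then "if we observe at most 12 objective responses we will not enroll any new participants". Otherwise, "If we observe 13 or more objective responses in the first stage, then we plan to enroll an additional 25 patients". The regimen counts as effective only if "there has to be objective responses in at least 29 patients". The section then gives operating characteristics at a true objective response rate of 41%: "we will have 66% chance of stopping the study early and, at most, 37 patients will be treated on the potentially ineffective therapy".

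Section 6.3 gives a maximum enrolment of 53 under Simon's minimax design. Table S1 lists a maximum sample size of 53 and, on a separate line, "Expected Sample Size If Response Probability = 0.64", with the value 33. It also gives an early-termination probability of 0.62 at that rate. The Synopsis and Section 3.1 likewise give 53 patients.

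**The concern.** A two-stage rule with one futility look can end at only two sizes: the first-stage size or the full size. In Section 6.7 these are 28 and 28 + 25 = 53. A ceiling of 37 is neither. It also conflicts with the stopping probability in the same sentence: if the trial stops early 66% of the time, it goes on to full enrolment the other 34% of the time.

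What is at stake is the stated exposure of patients to a regimen that does not work. Section 6.6 presents early stopping as the means of limiting that exposure, and Section 6.7 puts a number on it. If the number is an average presented as a cap, it errs in the reassuring direction.

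**Working it through.** **Inputs from Section 6.7.** First-stage size n1 = 28; stop if responses are 12 or fewer; second-stage size n2 = 25; true response rate p = 0.41. The final criterion of at least 29 responses does not affect how many patients are enrolled.

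**Step 1: reproduce the plan's stopping probability.** With X binomial (n = 28, p = 0.41),

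P(stop at 28) = P(X <= 12) = 0.6557.

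The plan prints 66%, so this reproduces.

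**Step 2: reproduce the 37.**

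E[N] = n1 + n2 x (1 - P(stop)) = 28 + 25 x (1 - 0.6557) = 28 + 25 x 0.3443 = 36.61, which rounds to 37.

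Using the plan's rounded 66% gives 28 + 25 x 0.34 = 36.5. The printed 37 therefore reproduces as an expectation. Neighbouring stopping limits fit neither printed figure: a limit of 11 gives a stopping probability of 0.508 and E[N] = 40.3, and a limit of 13 gives 0.782 and 33.4.

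**Step 3: the distribution of the sample size under the futility rule alone, at p = 0.41.**

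| Patients treated | Probability |
|---|---|
| 28 | 0.656 |
| 53 | 0.344 |

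The maximum is 28 + 25 = 53. The gap from the printed ceiling is 53 - 37 = 16 patients, and 16/37 = 43%.

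**Step 4: dependence on the response rate.** For the Section 6.7 rule:

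| True response rate | P(stop at 28) | E[N] | P(53 treated) |
|---|---|---|---|
| 0.35 | 0.857 | 31.6 | 0.143 |
| 0.40 | 0.695 | 35.6 | 0.305 |
| 0.41 | 0.656 | 36.6 | 0.344 |
| 0.64 | 0.018 | 52.5 | 0.982 |

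**Step 5: Table S1 as a control.** Its design has n1 = 20, stops at 13 or fewer responses, and has a maximum of 53. At p = 0.64:

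P(stop at 20) = P(X <= 13) = 0.6197 (printed 0.62).

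E[N] = 20 + 33 x (1 - 0.6197) = 20 + 33 x 0.3803 = 32.55 (printed 33, labelled as expected).

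P(53 treated) = 0.380.

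The same formula that yields Table S1's expected size yields the 37 in Section 6.7. Only the label differs.

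**The case against.** The arithmetic is hard to dispute. The best defence concerns wording and consequence, and much of it stands.

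- **The true maximum is in the plan.** The Synopsis, Section 3.1, Section 6.3 and Table S1 all give 53, and Table S1 also gives an expected size. A reader might infer that Section 6.7 is the plan's only account of possible exposure; it is not.
- **The chance of full enrolment can be worked out.** A reader might infer that the sentence conceals it. But the 66% is printed, so the 34% complement follows at once, and the same section says that 25 further patients are enrolled if the trial continues.
- **Nothing shows that anyone acts on the 37.** A reader might infer that the monitoring committee relies on it. Sections 5.3.1.1 and 6.3 describe quarterly summaries of serious adverse events going to that committee, with notification of individual events, and do not mention this figure. No boundary, enrolment cap or analysis uses it.
- **Roughly one trial in three is not a general figure.** A reader might apply it to ineffective regimens at large. It holds only near 41%: the share is 14.3% at 35% and 98.2% at 64%, the plan's own unpromising rate.
- **Section 6.8 adds other exits.** The toxicity boundaries are checked patient by patient and can end the trial at intermediate sizes, including 37. That qualifies the two-point distribution but does not make 37 a ceiling.
- **The words could be meant as a bound on the average for rates of 41% or lower.** The averages do fall as the rate falls. But the sentence speaks of patients treated and does not mention an average.
- **A larger defect overlaps this one.** Every figure in the sentence belongs to a rule that conflicts with Table S1 and must be revisited anyway. This is a good reason to report the two together. It does not make the sentence right: putting Table S1's 33 in place of 37 without changing the label would repeat the error.

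**Conclusion.** The sentence is wrong as written. At a 41% response rate, 37 is the expected sample size of the Section 6.7 rule (36.6), and the maximum is 53. The printed figure contradicts both the section's own 28 + 25 and the maximum in Section 6.3 and Table S1, and it understates worst-case exposure by 16 patients.

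The result assumes independent responses with a common rate of 41%, the Section 6.7 rule followed exactly, and no early stop for toxicity under Section 6.8. The toxicity assumption affects the probabilities 0.656 and 0.344; the maximum of 53 does not depend on it.

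Severity is minor. This is a mislabelled operating characteristic in one descriptive sentence. The documents do not support reading it as concealment, as a figure on which monitoring depends, or as a fault in the enrolment plan. It belongs beside the conflict between Section 6.7 (28 patients, stop at 12, at least 29 responses, 41%) and Table S1 (20 patients, stop at 13, more than 39 responses, 64%), which is the more serious matter.

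**What to change.** Reconcile Section 6.7 with Section 6.3 and Table S1. In the same edit, rewrite the exposure sentence so that it gives the stopping probability, the expected size and the maximum size as three separate quantities for the design that governs:

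- If the Table S1 design governs: at a 64% response rate, a 62% chance of stopping after 20 patients, with 33 patients treated on average and at most 53.
- If the Section 6.7 figures are kept: at a 41% response rate, a 66% chance of stopping after 28 patients, with 37 treated on average and at most 53.

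A short note that these figures leave out toxicity stopping under Section 6.8 would complete it. Changing only the label corrects this sentence but leaves the conflict between the two rules.

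The cost is one sentence. The stated exposure becomes less favourable. Relabelling the figure does not itself change the design or enrolment.

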3.1.1 Dose-Schedules

Patients will receive Dabrafenib (150 mg PO BID), Trametinib (2 mg PO QD) and Metformin (500 mg PO BID x 2 weeks, then 850 mg PO BID). Treatment will continue until progression, unless the patient experiences unacceptable toxicity. Patients will be evaluated for (1) clinical response, (2) safety, and (3) survival.

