6. STATISTICS

6.1 Study Design:

The study will be a single-arm, single center, uncontrolled phase I/II trial to estimate the safety of the combined treatments and then estimate the efficacy in terms of objective response (CR+PR) rate in patients with stage IIIC and Stage IV melanoma treated with dabrafenib/trametinib and metformin.

6.2 End-Point Definitions:

We will use two main end points. The primary endpoint of interest is the clinical response as defined in Section 5. The second end point will be tolerability to treatment. Secondary end points to be considered are the overall survival, OS, which is the time to first event or death due to any reason.

6.3 Sample Size:

The study is conducted in 2 phases.

Phase I:

In phase I, we will enroll 6 patients for the combination regimen of Dabrafenib/Trametinib/Metformin. We will allow at the most two drug-related CTCAE grade 4 toxicities in 6 patients in order to advance to Phase II. If we observe any drug-related deaths or more than two drug-related CTCAE grade 4 events, then we will halt the trial.

The Data and Safety Monitoring Plan of the Brown Cancer Center will be used for this phase I/II protocol. The investigators will conduct continuous review of data and patient safety at weekly meetings where the results of each patient's treatment are discussed. The discussion will include the number of patients, significant toxicities as described in the protocol, dose adjustments, and responses observed. Quarterly summaries of SAEs will be submitted through the CTO to the DSMC for review.

Phase II:

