The cumulative number of grade 3 or 4 toxic events will be monitored after each person is enrolled^{32, 33}. If the cumulative number of toxic events produces enough evidence to conclude that the true toxicity rate is greater than or equal to 33% ($Pt_0 = 0.33$) then the trial will be stopped early for safety reasons. The cumulative number of toxic events after each person is treated will be compared to the boundary values in Table S2. If the cumulative number of toxic events after person is treated is greater than or equal to the associated boundary value b_i then the combination treatment is rejected for safety considerations. With this rule, there is only a 5% chance of stopping the trial early for lack of safety if the true toxicity rate is less than 33%. Continual assessment of the toxic events ensures we do not expose an undue number of patients to a harmful treatment.

Table S2. Toxicity Boundaries, $N = 53$, $Pt_0 = 0.33$, and $\alpha = 0.05$

Minimum Number of Subjects	Maximum Number of Subjects	Number of Toxicities
4	4	4
5	6	5
7	7	6
8	9	7
10	11	8
12	14	9
15	16	10
17	18	11
19	19	12
20	22	13
23	23	14
24	27	15
28	28	16
29	30	17
31	32	18
33	34	19
35	37	20
36	40	21
41	42	22
43	45	23
46	47	24
48	50	25
51	52	26
53	54	27

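### Section 6.8 counts grade 3-4 toxic events, but Table S2 comes near its stated 5% only if each patient counts once; the table also gives two boundaries at n = 36 and 37

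*Combined protocol and SAP*

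**What the plan says.** Section 6.8 describes continuous toxicity monitoring for the combined Phase I/II trial: "The cumulative number of grade 3 or 4 toxic events will be monitored after each person is enrolled". The decision step uses the same quantity: "The cumulative number of toxic events after each person is treated will be compared to the boundary values in Table S2". The combination is rejected when the count reaches or exceeds the boundary. The null toxicity rate is 33%, and for true rates below it the section claims "there is only a 5% chance of stopping the trial early for lack of safety".

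Table S2 is indexed by minimum and maximum number of subjects, and its boundary column is headed as a number of toxicities. It starts at 4 toxicities in 4 subjects and ends at 27 for 53-54 subjects. Two of its rows are 35-37 subjects (boundary 20) and 36-40 subjects (boundary 21).

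Two other places bear on how toxicities accumulate. Section 3.1.1 says "Treatment will continue until progression, unless the patient experiences unacceptable toxicity", so one patient may be observed over many cycles. Section 6.5 treats toxicity as a dichotomous outcome, but only in an exploratory regression.

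**The concern.** A count of events and a count of patients are different quantities once any patient has a second grade 3 or 4 event. The boundary is built for a proportion of subjects, while the operative sentences tally events and set no limit per patient. Adverse events are graded and documented one by one (Section 5.3.1) and collected at every cycle, so a tally taken from the adverse event log would naturally be an event count.

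For example, suppose ten patients have been treated, five have had a grade 3 or 4 toxicity, and three of those five have had a second. The event count is 8, which equals the boundary at n = 10, and the trial stops. The patient count is 5, three below the boundary, and it continues.

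What is at stake is a false stop: an acceptable regimen could be rejected because of a counting convention. Toxicity would not go undetected, because an event count is never smaller than a patient count. The overlapping rows add a second point at which the rule does not give a single decision.

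**Working it through.** **Inputs from Section 6.8 and Table S2.** Null rate p = 0.33; maximum n = 53; a look after every patient; stop when the count is at or above b(n). At n = 36-37, b is taken as 20 and then as 21.

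**Step 1: the plan's own figure, one count per patient.** Let f(n,k) be the probability of k toxicities after n patients without an earlier stop. Then

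f(n,k) = f(n-1,k)(1-p) + f(n-1,k-1)p.

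At each look, the mass at k ≥ b(n) is added to the stop probability and removed. The first terms can be checked by hand:

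- n = 4 (4 of 4): 0.33^4 = 0.0119.
- n = 6 (5 of 6, the one unaffected patient being among the first four): 4 × 0.33^5 × 0.67 = 0.0105.

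These sum to 0.0223. The recursion to n = 53 gives:

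| True patient rate | b = 20 at n = 36-37 | b = 21 at n = 36-37 |
|---|---|---|
| 25% | 1.01% | 1.01% |
| 30% | 3.01% | 3.00% |
| 33% | 5.67% | 5.65% |
| 40% | 21.3% | 21.2% |

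The 5% level is crossed at a true rate of about 32.4%. The stated 5% is therefore nearly, though not exactly, met when each patient counts once.

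**Step 2: the same boundaries with events counted.** The documents give no number of grade 3-4 events per affected patient. Assumption: an affected patient has 1 + Poisson(m) events. A rough check at the last look: 0.33 × 53 = 17.5 affected patients are expected against a boundary of 27. With m = 0.5 the expected event count is 17.5 × 1.5 = 26.2, almost at the boundary.

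Timing also matters, so three patterns were taken. In the first, all of a patient's events fall at that patient's own place in the sequence (exact convolution; an upper extreme). In the other two, the extra events are spread evenly over the next 0-25 or 0-50 enrolments (simulation). At the accrual of 30 patients per year in Section 6.4, 25 enrolments take 25/30 of a year (10 months) and 50 take 20 months. Stop probabilities at a 33% patient rate:

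| Extra events per affected patient (m) | No delay | Spread 0-25 | Spread 0-50 |
|---|---|---|---|
| 0.1 | 18% | 11% | 8% |
| 0.25 | 40% | 22% | about 14% |
| 0.5 | 70% | 45% | 28% |

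The probability reaches 10%, double the stated level, at about 4, 9 and 14-15 extra events per 100 affected patients respectively. At a 25% patient rate with the 0-25 spread, it is 1.9%, 4.4% and 13% for the three values of m, against 1.0% counting patients.

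**Step 3: the overlap.** No n from 4 to 53 other than 36 and 37 is duplicated or missing. The choice between 20 and 21 changes the overall stop probability at 33% by 5.67 - 5.65 = 0.02 percentage points. The chance of having exactly 20 toxicities at n = 36 or 37 without an earlier stop is 0.11% at a 33% rate and 0.82% at 40%.

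**The case against.** The strongest reply is that the intention is clear. Section 6.8 speaks of a true toxicity rate tested against 33%, the table is indexed by subjects, and its first boundary is 4 of 4 with none for n = 1-3. That pattern fits at most one toxicity per subject, and Section 6.5 calls toxicity dichotomous. On that reading the boundaries are sound and only a definition is missing. This is right about the intention, but the sentences that people will apply still say events, and none of these hints defines the monitored count.

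The larger percentages do rest on assumed event rates and timing, and most are computed at the edge of the null. Stopping treatment for unacceptable toxicity (Section 3.1.1) and dose modification (Section 4.8) could limit repeat events. At a 25% patient rate, two of the three figures stay below 5%. These limits stand: the size is a range under stated assumptions, not an estimate for this trial.

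The trial is single-centre with weekly review, which makes inconsistent counting less likely but does not say which count is used. The overlap may be a one-digit slip or an error in reading the PDF, and its effect on error is trivial. That also stands; it needs a check against the source.

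**Conclusion.** The concern holds. As worded, Section 6.8 monitors events against a boundary that comes near its stated error only when patients are counted: 5.7% at a 33% rate. Under literal event counting with 0.1 to 0.5 extra events per affected patient, the false-stop probability at 33% runs from 8% to 28% with the slowest spread and from 18% to 70% with no delay. These figures rest on the assumed 1 + Poisson(m) form and on the assumed timing. The boundaries themselves need no redesign, and the 5.7% against 5% is minor.

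The two boundaries at n = 36 and 37 are a contradiction in the table as supplied, with negligible effect on overall error.

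Two secondary gaps do not affect this conclusion. The Phase I rule in Section 6.3 is limited to drug-related events, while Section 6.8 does not say whether relatedness is required. The rule on drug-related deaths ("If we observe any drug-related deaths or more than two drug-related CTCAE grade 4 events, then we will halt the trial") is written for Phase I, and Section 6.8 counts grade 3 or 4 only. The centre's Data and Safety Monitoring Plan is not part of these documents and may cover later deaths.

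**What to change.** - In Section 6.8, define the monitored count as the number of patients with at least one grade 3 or 4 toxicity, each counted once and indexed to patients treated.
- In the same sentence, state whether the toxicity must be drug-related.
- Check rows 35-37 and 36-40 of Table S2 against the source calculation and reconcile them so that every n has a single boundary.
- State the error rate as about 5.7% at a true rate of 33% (minor).
- Reconcile Section 6.8 with the Phase I rule on drug-related deaths in the synopsis and Sections 6.3 and 6.5, or cite the part of the Data and Safety Monitoring Plan that applies, so the text says how such a death after Phase I enters monitoring.

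The cost is one or two sentences and one table row, plus a cross-reference if needed. No patients or visits are added. No new boundary or clinical rule is proposed here.

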4. STUDY TREATMENTS

4.1 Treatments Administered

Patients will receive Dabrafenib (150 mg PO BID), Trametinib (2 mg PO QD) and Metformin (500 mg PO BID x 2 weeks, then 850 mg PO BID). Treatment will continue until progression, unless the patient experiences unacceptable toxicity. Patients will be evaluated for (1) clinical response, (2) safety, and (3) survival.

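### Section 6.8 gives two conflicting triggers for the Table S2 toxicity looks and no observation window; if looks fall at enrollment, the rule detects an unsafe rate less often

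*Combined protocol and SAP*

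**What the plan says.** Section 6.8 opens with the schedule: "The cumulative number of grade 3 or 4 toxic events will be monitored after each person is enrolled". It then describes the comparison itself: "The cumulative number of toxic events after each person is treated will be compared to the boundary values in Table S2". If the count "is greater than or equal to the associated boundary value b_i then the combination treatment is rejected for safety considerations". The table is headed "Toxicity Boundaries, $N = 53$, $Pt_0 = 0.33" with a 5% level, is indexed by number of subjects, and comes with the statement that "there is only a 5% chance of stopping the trial early for lack of safety" when the true rate is below 33%.

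Sections 3.1.1 and 4.1 continue treatment until progression or unacceptable toxicity. No section defines a toxicity observation window, an evaluability rule or an accrual hold.

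The Phase I gate is a separate rule. Section 6.3 states: "We will allow at the most two drug-related CTCAE grade 4 toxicities in 6 patients in order to advance to Phase II". Section 6.5 adds that six consecutive patients are to be evaluated, without saying for how long. Section 4.1 gives "Metformin (500 mg PO BID x 2 weeks, then 850 mg PO BID", so the dose steps up after two weeks. Section 6.4 states: "Based on our experience we plan to enroll 30 patients per year".

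**The concern.** A boundary of the Table S2 kind compares a count of toxicities with the number of patients who could have contributed to it. If patients are added to the denominator on the day they enroll, the boundary rises at once while their toxicities arrive later. The rule then lags behind the data.

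The *treated* wording does not settle the matter, because treatment has no fixed end. Two people applying Section 6.8 in good faith could look at different times, with different denominators, and reach different stopping decisions. Sections 6.6 and 6.8 give early stopping, and limiting exposure to a harmful regimen, as the purpose of the rule, and a lag works against that purpose.

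The Phase I gate has a related gap. Without a stated evaluation period, the decision to advance could rest partly on a patient who has not yet reached the metformin step.

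**Working it through.** **Inputs from the plan.** Table S2 boundaries b_n, with stopping when the count is at least b_n; N = 53; null rate 33%; 30 patients per year (6.4); metformin step after 2 weeks (4.1). Rows 35–37 and 36–40 of Table S2 overlap. I read the second as 38–40; the other reading changes the result at 33% by less than 0.001.

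**Assumptions, because the plan gives no figure.** True unsafe rates of 50% and 60%; at most one counted toxicity per patient; onset uniform over 4 or 8 weeks; random (exponential) gaps between enrollments.

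**1. The plan's own 5%.** Let f_n(k) be the probability of reaching patient n without stopping and with k toxicities. Then f_n(k) = (1−p)·f_{n−1}(k) + p·f_{n−1}(k−1) for k < b_n, and any mass at k ≥ b_n is the probability of stopping at n. With every patient's outcome known at each look:

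- p = 0.32: P(stop) = 0.046
- p = 0.33: P(stop) = 0.057
- p = 0.50: P(stop) = 0.682
- p = 0.60: P(stop) = 0.967

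The stated 5% is approximately, not exactly, reproduced, and only under completed outcomes.

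**2. Effect of a fixed lag (exact).** At look n, keep b_n but count only the first n − L patients. At p = 0.50:

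| Lag L | P(stop) | P(stop by patient 20) |
|---|---|---|
| 0 | 0.682 | 0.335 |
| 1 | 0.608 | 0.218 |
| 2 | 0.536 | 0.132 |
| 3 | 0.467 | 0.073 |

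For scale, the mean gap is 365.25/30 = 12.2 days, so about 28/12.2 = 2.3 patients enroll in 28 days.

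**3. Looks at enrollment (simulation).** Late toxicities are credited at later looks.

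| True rate | Completed outcomes | Enrollment looks, 4-week onset | Enrollment looks, 8-week onset |
|---|---|---|---|
| 33% | 0.057 | about 0.02 | about 0.015 |
| 50% | 0.68 | about 0.56 | about 0.50 |
| 60% | 0.97 | 0.93–0.94 | about 0.91 |

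Mean enrollment at 50% is about 40 (4 weeks) or 43 (8 weeks) with enrollment looks, against 35 or 36 when each look waits for the window. The latter figures include patients who enroll while a window is pending.

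**4. A milder reading of *treated*.** Suppose each look falls just before the next enrollment, with a last comparison at full follow-up. P(stop) at 50% is then about 0.64 (4 weeks) or 0.60 (8 weeks). The loss is smaller but remains.

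**5. Phase I gate.** At the mean gap, when patient 7 arrives the six patients have about 73, 61, 49, 36, 24 and 12 days of exposure. Patient 6 is about 2 days short of day 14. With random arrivals, P(gap < 14 days) = 1 − exp(−14/12.175) = 0.68. To show what a missing outcome does, take an illustrative 33% grade 4 rate and at most one event per patient: P(at most 2 events) is 0.687 if six patients contribute and 0.795 if only five do.

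**The case against.** The strongest reply is that Section 6.8 is not settled on enrollment. *Enrolled* appears once, in the introductory sentence; the sentences that apply the boundary say *treated*. That stands. A reader might infer that the protocol prescribes enrollment looks, or that toxicity arising after patient 53 enrolls is never compared with a boundary. The text supports neither as a fixed rule. It supports a contradictory and undefined trigger.

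Second, the sizes rest on assumptions. The plan gives no onset window, no unsafe alternative and no target power, so a reader who concludes that Table S2 falls short of a promised detection rate goes too far. Nor is the 5% breached by late looks: a false-stop probability of 0.015–0.02 lies within it as an upper limit. At 60% most trials still stop.

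Third, Section 6.8 refers to toxic events and does not limit them to one per patient. If each toxic patient has on average 0.25 further events (an assumption), enrollment looks with an 8-week window stop about 90% of trials at a 50% rate and about 25% at 33%. The levels above therefore depend on the counting convention. The direction does not: under any one convention, toxicities seen among the first n patients at enrollment n cannot exceed those seen among the same patients once their windows are complete.

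Fourth, for Phase I, five of the six patients would be past two weeks at the mean gap, and the lower starting dose is itself part of the regimen. Reading the plan as prescribing that Phase II opens before patient 6 steps up is not supported: Section 6.5 requires six patients to be evaluated. Early opening is possible, not prescribed.

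Weekly safety meetings (5.3.1.1, 6.3) mitigate in part, but they carry no boundary comparison and no follow-up requirement.

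**Conclusion.** The concern holds as an undefined look time for a formal stopping rule. Section 6.8 contains two triggers that conflict, neither fixes a date, and Table S2 has about its stated error rate only with completed outcomes (0.057 at 33%).

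Under the enrollment reading, the stopping probability at a 50% rate drops by about 0.12 (0.68 − 0.56) to 0.18 (0.68 − 0.50), and about 5 (40 − 35) to 7 (43 − 36) more patients are enrolled on average. At 60% the drop is about 0.03 to 0.06. These sizes are illustrative. They assume the stated accrual, one toxicity per patient and uniform onset over 4 to 8 weeks.

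The Phase I gap is a separate and smaller point. The evaluation period is unstated, and at planned accrual the decision could precede patient 6's metformin step.

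**What to change.** In Section 6.8:

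- Reconcile the two wordings into one trigger.
- Define a toxicity observation window, its length chosen by the sponsor, ending at a visit already in Appendix 1.
- Index Table S2 by patients who have completed that window.
- State how toxicities already seen in patients still inside the window are counted, and whether the count is of patients or of events. Recompute the 5% under that convention, since adding such toxicities without their patients would raise it.
- Add a final comparison when the last patient completes the window.

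In Sections 6.3 and 6.5, state the evaluation period that all six patients must complete, or stop early for toxicity, before the Phase I decision. Reconcile that period with the dosing schedule in Section 4.1.

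The change takes a few sentences, with no new visits, no added patients, and no change to thresholds or doses. The cost is a possible short accrual hold after patient 6. Purely for scale, a period of 28 days would mean a hold of about 28 − 12.2 ≈ 16 days at planned accrual.

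### Counting each patient at most once, Table S2's printed boundaries stop a regimen with a true 33% toxicity rate 5.7% of the time, not the stated 5%

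*Combined protocol and SAP*

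**What the plan says.** Section 6.8 covers safety monitoring for the combined Phase I/II trial. On what is counted, it says: "The cumulative number of grade 3 or 4 toxic events will be monitored after each person is enrolled". On how often: "The cumulative number of toxic events after each person is treated will be compared to the boundary values in Table S2". On the action: if the count "is greater than or equal to the associated boundary value b_i then the combination treatment is rejected for safety considerations".

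The table headed "Table S2. Toxicity Boundaries" is labelled N = 53, Pt0 = 0.33 and alpha = 0.05. Its first boundary is at patient 4. Section 6.8 summarises the rule's performance in one sentence: "there is only a 5% chance of stopping the trial early for lack of safety if the true toxicity rate is less than 33" per cent.

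The section does not name the type of boundary, give the level of any single look, or say that a patient with several qualifying events counts once. Two rows overlap: 35–37 (boundary 20) and 36–40 (boundary 21) both cover patients 36 and 37.

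**The concern.** The 5% false-stop rate is the only operating characteristic given for this rule. It can be checked from the printed table alone, because the limit, the number of patients, the boundaries and the look schedule are all there. The natural test point is 33%: it is the table's own Pt0, and a bound claimed for every rate below 33% must also hold as the rate approaches 33%.

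If the table does not deliver 5%, a committee or ethics board relying on Section 6.8 has a slightly wrong idea of how often an acceptable regimen would be stopped by chance. What is at stake is the accuracy of a stated property. The 33% limit itself is not in question.

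**Working it through.** **Inputs.** From Section 6.8 and Table S2: limit p = 0.33; N = 53; boundary b(n) for n = 4 to 53; stop when the count is at or above b(n); a look after every patient. Assumptions not stated in the plan: one yes/no toxicity outcome per patient, outcomes complete at each look, and monitoring able to run to patient 53.

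**Method.** Let f(n, k) be the probability of having k toxicities after n patients without having stopped. Then f(n, k) = f(n−1, k)(1−p) + f(n−1, k−1)p. Whenever k ≥ b(n), that probability is removed and added to P(stop). This is exact.

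**Trying to reproduce the plan's 5%.** At p = 0.33:

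| Reading | P(stop) |
|---|---|
| As printed, boundary 20 at n = 36–37 | 5.67% |
| As printed, boundary 21 at n = 36–37 | 5.65% |
| Run to N = 52 | 5.67% |
| Run to N = 54 | 5.7% |
| Stop only when the count exceeds b(n) | 1.6% |
| Looks only from patient 7 | 4.5% |

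None of these gives 5%. A simulation of one million trials gave 5.64% for the printed rule, in line with the exact value.

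**By true rate (printed rule).**

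| True rate | P(stop) |
|---|---|
| 25% | 1.0% |
| 30% | 3.0% |
| 32% | 4.6% |
| about 32.4% | 5.0% |
| 33% | 5.7% |

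**Where the excess comes from.** The two earliest contributions can be checked by hand:
- Patient 4, 4 of 4: 0.33^4 = 0.0119.
- Patient 5 adds nothing, because 5 of 5 requires 4 of 4 first.
- Patient 6, 5 of 6 without an earlier stop: 3 of the first 4, then both of the next 2, so 4 × 0.33^3 × 0.67 × 0.33^2 = 0.0105.

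Together they spend 0.0119 + 0.0105 = 0.0224, or 2.2 of the 5.7 points. Patients 14, 16, 18 and 27 add 0.0057 + 0.0034 + 0.0025 + 0.0025 = 0.0141.

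Removing the stop at 4 of 4 and requiring one more event at patient 6, as a diagnostic only, gives 4.6%. The fall is less than 2.2 points because some of those paths cross a later boundary instead.

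**Futility sensitivity.** Suppose accrual can end at the Table S1 look (13 or fewer responses in 20) and response is independent of toxicity. By patient 20, 0.0414 of the 0.0567 has been spent, leaving 0.0153.
- Response rate 0.64: the early-termination probability is 0.62, so 0.0414 + 0.38 × 0.0153 = 4.7%.
- Response rate 0.80: it is 0.087, so 0.0414 + 0.913 × 0.0153 = 5.5% (0.0554 from unrounded values).

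**The case against.** The strongest defence is that the sentence in Section 6.8 speaks of rates below 33%, and for nearly all of them it is true: the rate of false stops is 5% or less up to about 32.4%. The excess at the limit is 0.7 points, and for a safety rule it lies on the cautious side. The figure is also conditional: allowing for the Table S1 futility look gives about 4.7% to 5.5%. All of that stands, and it is why the point is minor. It does not remove it. The table is labelled alpha = 0.05 at Pt0 = 0.33, and the plan does not present its 5% as allowing for a futility stop. Counting each patient once favours the plan: if one patient could add several events, then at the same per-patient rate false stops could only be more frequent.

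A reader might infer two stronger things.

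- **That the excess arises because the level varies from look to look.** It does vary, from 0.0024 (7 of 8) to 0.0170 (5 of 6), but that is not the cause. Tightening only patients 4 and 6 gives 4.6% with the rest of the table still uneven. A boundary with a constant cap on each look's level gives 4.5% at a cap of 0.0118, 5.06% at 0.0119 and 6.0% at 0.015. What matters is how lenient particular looks are.
- **That the table is insensitive and should be replaced by a constant-level one.** The documents require no such boundary. A version capped at 0.0114 stops slightly more often at a true 50% rate (70.1% against 68.2%), but it removes or raises the earliest stops and treats more patients on average (34.2 against 32.8).

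**Conclusion.** The point holds as a minor labelling error. At the table's own limit of 33%, the printed boundaries stop the trial with probability 5.7%, not 5%. This assumes one count per patient, a look after every patient with complete outcomes, and monitoring that can run to patient 53. The choice between the overlapping rows changes the figure by only 0.02 points. The stated 5% fails only for true rates between about 32.4% and 33%. The documents do not support reading this as a safety hazard or as a reason to prefer a particular boundary shape.

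**What to change.** In Section 6.8 and in the Table S2 heading, replace the 5% and alpha = 0.05 with the exact level, about 5.7% at a true rate of 33%. State beside it the assumption that each patient counts at most once. Reconcile rows 35–37 and 36–40, and quote the level for the table as reconciled. This costs one number, one sentence and one row correction, and leaves the 33% limit alone.

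If the sponsor wants a true 5%, its statistician should recalibrate the table with a boundary type of the sponsor's choice, name that type, and report the exact level achieved. That costs one recomputed table. No specific replacement boundary is proposed here.
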